## 6. STUDY PROCEDURES

### 6.1 Study Schedule

The study will consist of a Screening Period, a Treatment period and a Post-treatment follow-up period. These periods are described below.

All required study procedures are outlined in [Appendix A](#).

#### 6.1.1 Screening

Written informed consent for the study will be obtained prior to the performance of any study-related procedures including screening procedures. An up to 5-week period is provided for completing screening assessments and determining subject eligibility for the study. During the Screening Period, subject will be advised to maintain diet and exercise routines and remain on a stable regimen of diabetes and lipid medications (if they are already taking any).

Subjects will undergo a medical history, including collection of race and ethnicity, physical examination including vital signs, 12-lead ECG, and have blood and urine samples taken for clinical laboratory testing. Subjects will be screened for HIV, hepatitis B, and hepatitis C. Safety labs may be retested for determination of subject eligibility after consultation with the Sponsor Medical Monitor.

As part of the Screening Period, subjects not already on a stable diet will have 4 weeks of diet run-in, followed by a qualification visit, during which final eligibility assessments will be performed. Subjects on stable diet known to the investigator and followed at the site may go from screening to qualification without a 4-week diet run-in. At the qualification visit TGs will be measured. MRI will be obtained during screening once all other eligibility criteria are met to assess liver fat content.

On confirmation of eligibility and prior to randomization, subjects will also undergo a 24 hr urine collection for creatinine, albumin, and protein as a Qualification assessment.

### **6.1.2 Treatment Period**

During the treatment period, eligible subjects will be randomized and report to the Study Center for clinic visits. Subjects will be randomized to 1 of 3 dose cohorts and receive 20 mg doses of Study Drug administered by SC injection once per week (weekly) for 26 weeks in Cohort A, 40 mg doses of Study Drug administered by SC injection once every 4 weeks for 21 weeks in Cohort B, and 80 mg doses of Study Drug administered by SC injection once every 4 weeks for 21 weeks in Cohort C ([Section 8.1](#)).

Collection and measurement of vital signs, physical examination results, ECGs, clinical laboratory parameters ([Appendix B](#)), ISIS 703802 plasma concentrations, immunogenicity and biomarker samples, AEs and concomitant medication/procedure information will be performed according to the Schedule of Procedures in [Appendix A](#).

#### Extensive Pharmacokinetic (PK) Subgroup Only:

Within each cohort, a subgroup of approximately 12 subjects, who will consent to voluntary extensive PK sampling, will undergo additional PK sampling, in what is referred to as the PK Subgroup in this study. Subjects in this subgroup will have additional PK sampling time points in order to evaluate the plasma PK parameters of ISIS 703802. Subjects in this subgroup will have additional visits to the clinic during the treatment period in order to collect blood samples for PK assessment ([Appendix A](#) and [C](#)).

### **6.1.3 Post-Treatment Period**

Each subject will be followed for safety assessments for 13 weeks after the Treatment Period (last dose through one dosing interval post last dose). During the post-treatment evaluation period, subjects will return to the Study Center for outpatient visits as outlined in [Appendix A](#) for safety and clinical laboratory evaluations.

## **6.2 Study/Laboratory Assessments**

Laboratory analyte samples will be collected throughout the Study. A list of these analytes is contained in [Appendix B](#).

Blood chemistry and urine samples (excluding 24-hour urine collection) should be taken after fasting for 10 hours. Any confirmatory test, or test taken for safety reasons, may be taken at any time, irrespective of fasting status. During this time subjects can drink water and should ensure that they consume sufficient water to not become dehydrated.

If tests are uninterpretable (e.g., due to clumping, hemolysis or quantity not sufficient) or missing, a repeat blood or urine specimen should be re-drawn as soon as possible (ideally within 1 week).

While on treatment hematology samples will be collected every 14 days +/- 2 days. Each time a hematology lab is drawn and sent to the central laboratory for analysis, an additional sample should be collected in parallel and analyzed locally. In the event that both the central and local samples are unreportable (e.g., due to hemolyzed or clumped blood samples), subject dosing cannot continue until another sample is repeated and determined not to have met a platelet stopping rule.

If there is no reportable platelet count within 14 days of the last platelet count, the Investigator will contact the subject to hold dosing until a new platelet count is obtained and reviewed.

While on treatment, blood samples for liver function testing will be collected every 14 days +/- 2 days and sent to the central laboratory for analysis for the first 3 months of the study treatment, and monthly thereafter during the Treatment Period per [Section 8.5.1](#).

While on treatment, blood and urine samples for renal function testing will be collected every 14 days +/- 2 days and sent to the central laboratory for analysis for the first 3 months of the study treatment, and monthly thereafter during the Treatment Period per [Section 8.5.2](#).

All lab samples are to be sent to the central laboratory by overnight courier and processed. Lab Alerts issued as per protocol safety monitoring requirements or stopping rules will indicate the applicable protocol section to facilitate review and will be immediately and simultaneously sent by email to the Investigator, the Sponsor and the CRO Medical Monitors, the Sponsor Drug Safety Physician, and the Clinical Trial Manager (CTM), and should be received by them within 2 days from sample collection. Hematology results from the site's local laboratories are received by the Study Center staff per the local laboratories' standard reporting time and should be entered as soon as possible into the eCRF to inform the Sponsor and CRO study monitoring teams.

All platelet count results must be reviewed promptly (within 48 hours of receipt) by the Investigator, or designee, to ensure that the count has not met the stopping rule and to determine whether the rate of decline is suggestive that the subject could be approaching the dose interruption rule of 75,000/mm^3 as specified in [Section 8.6.3](#). Any case of a platelet count reduction to levels below 50,000/mm^3 is considered an adverse event of special interest and must be reported in an expedited fashion to the Sponsor as per [Sections 9.3.3](#) and [9.4.1](#).

All liver and renal function tests must also be reviewed promptly (within 48 hours of receipt) by the Investigator, or designee, to ensure that the result has not met the stopping rule. Any event meeting renal stopping rules criteria described in [Section 8.6.2](#) is considered an adverse event of special interest and must be reported in an expedited fashion to the Sponsor as per [Sections 9.3.3](#) and [9.4.1](#).

All lab alerts received, including those related to platelet, liver, or renal function monitoring/stopping rules, are also reviewed promptly by the Sponsor and the CRO Medical Monitors who will agree on actions to be taken. Within 24 hours of receiving an actionable lab alert the CRO Medical Monitor will communicate instructions to the Investigator and the study

personnel by emailing them the Safety Surveillance Form that needs to be signed by the Investigator/study personnel and promptly returned to the Sponsor and CRO Medical Monitor. In urgent cases, such as platelet results below 50,000/mm^3, or liver or renal test results reaching a critical stopping rule the Investigator must also be contacted by phone.

Further information on safety monitoring and actions to be taken by the Study Investigator in the event of reduced platelet count are provided in [Sections 8.5.3](#) and [8.6.3](#).

### **6.2.1 Physical Exams and Vital Signs**

Physical exams and vital signs will be performed as indicated in the Schedule of Procedures ([Appendix A](#)). Vital signs should include weight, blood pressure (BP), pulse rate, respiratory rate and body temperature. BP and pulse rate will be recorded after the subject has been in a sitting position for at least 5 minutes. BP should always be measured on the same arm (preferentially on the left arm). Height will be measured at Screening.

### **6.2.2 Electrocardiography**

Electrocardiography (ECG) will be conducted at Screening, Day 1, (prior to the first dose of Study Drug), and again during the treatment period as follows per dosing cohort:

- Cohort A at Weeks 5, 13, 21, and 27/ET
- Cohorts B and C at Weeks 5, 13, 21 and 25/ET

In all cohorts, ECGs will be conducted during the post-treatment follow-up period at scheduled visits.

ECGs will be recorded after the subject has been resting in a supine position for at least 5 minutes. ECGs will be performed in triplicate.

### **6.2.3 PK Sampling**

Blood samples for the determination of plasma ISIS 703802 concentrations will be collected prior to dosing on Day 1 and at various times throughout the treatment and post-treatment follow-up periods as noted in the tables in [Appendix C](#).

Within each cohort, subjects assigned to the PK Subgroup will have additional PK sampling time points and additional visits to the clinic during the treatment period in order to collect blood samples for PK assessment ([Appendix C](#)).

## **6.3 Restriction on the Lifestyle of Subjects**

### **6.3.1 Contraception Requirements**

All male subjects and women of childbearing potential must refrain from sperm/egg donation and either be abstinent† or practice effective contraception from the time of signing the informed consent form until at least a period of 13 weeks after their last dose of study treatment.

Male subjects engaged in sexual relations with a female of child-bearing potential must also encourage their female partner to use effective contraception from the time of signing the informed consent until a period of 13 weeks after the subject's last dose of study treatment.

For the purposes of this study, women of childbearing potential are defined as any female who has experienced menarche, and who does not meet one of the following conditions:

- Postmenopausal: 12 months of spontaneous amenorrhea in females > 55 years of age or, in females ≤ 55 years, 12 months of spontaneous amenorrhea without an alternative medical cause and FSH levels in the postmenopausal range for the laboratory involved
- 6 weeks after surgical bilateral oophorectomy with or without hysterectomy
- Post hysterectomy

For the purposes of the study, effective contraception is defined as follows:

For male subjects:

- Effective male contraception includes a vasectomy with negative semen analysis at follow-up, or the use of condoms together with spermicidal foam/gel/film/cream/suppository
- Male subjects with partners that are pregnant must use condoms as contraception to ensure that the fetus is not exposed to the Study Drug

For female subjects and female partners of male subjects:

- Using 2 of the following acceptable methods of contraception: surgical sterilization (e.g., bilateral tubal ligation), hormonal contraception, intrauterine contraception/device, or any 2 barrier methods (a combination of male or female condom\* with diaphragm, sponge, or cervical cap) together with spermicidal foam/gel/film/cream/suppository

†**Note:** Abstinence is only acceptable as true abstinence, i.e., when this is in line with the preferred and usual lifestyle of the subject. Periodic abstinence (e.g., calendar, ovulation, symptothermal, post-ovulation methods), declaration of abstinence for the duration of a trial and withdrawal are not acceptable methods of contraception.

**\*Note: A female condom and a male condom should not be used together as friction between the two can result in either or both products failing.**

### 6.3.2 *Other Requirements*

All subjects will be required to fast for at least 10 hours before visits requiring fasted blood sampling.

## 7. STUDY DRUG

### 7.1 Study Drug Description

Study Drug (ISIS 703802 or Placebo) characteristics are listed in [Table 1](#).

Study Drug (ISIS 703802 or Placebo) will be provided as 0.8 mL deliverable volume in 2 mL stoppered and sealed glass vials as a sterile solution.

The Study Drug is clear to slightly yellow in color, it is for single use, contains no preservatives and must be stored between 2 to 8 °Celsius and be protected from light.

**7.1.1 ISIS 703802 (ISIS 703802)**

ISIS 703802 vials contain 100 mg/mL ISIS 703802 in water for injection. Additionally, sodium phosphate buffer and sodium chloride are added to control the measure of the acidity or basicity of the solution (pH) and tonicity, respectively. The target pH is 7.4.

**7.1.2 Placebo**

Placebo vials contain 0.9% sodium chloride in water for injection. 1.6 µg/mL riboflavin is added to ensure color matching of placebo vials to ISIS 703802 vials.

**Table 1 Study Drug Characteristics**

Study Drug	ISIS 703802	Placebo
Strength	100 mg/ mL	Not Applicable
Volume/Formulation	0.8 mL/ per 2.0 mL vial	0.8 mL/ per 2.0 mL vial
Route of Administration	SC*	SC*

\* SC = subcutaneous

**7.2 Packaging and Labeling**

The Sponsor will provide the Investigator with packaged Study Drug (ISIS 703802 or placebo) labeled in accordance with specific country regulatory requirements.

**7.3 Study Drug Accountability**

The study staff is required to document the receipt, dispensing, and return of Study Drug (ISIS 703802 or placebo) supplies provided by the Sponsor. The subject must return all used and unused Study Drug to the Study Center for accountability. The Study Center must return all used and unused Study Drug to the Sponsor or designee. All used syringes must be disposed of as per the site’s hazardous waste destruction policy.

**8. TREATMENT OF SUBJECTS**

**8.1 Study Drug Administration**

Study Drug (ISIS 703802 or placebo) will be administered to subjects by Study Center staff as follows:

Cohort A: a single SC dose of 20 mg every week (weekly) for 26 weeks and 26 doses

Cohort B: a single SC dose of 40 mg once every 4 weeks for 21 weeks and 6 doses

Cohort C: a single SC dose of 80 mg once every 4 weeks for 21 weeks and 6 doses

Self-administration, if applicable, will be allowed after appropriate training of subject and/or caregiver.

Subjects in Cohort A receive 1 dose per week, and subjects in Cohorts B and C should receive 1 dose every 4 weeks with weeks always defined relative to Study Day 1. For example, if a

subject receives the first dose on a Monday, subsequent doses should be given on Mondays according to the respective dosing schedule, if possible. If a subject misses an injection, or if dosing on the usual day is not possible, the subject can reschedule the injection provided that 2 doses are administered at least 2 days apart.

Every effort should be made to ensure the previous dose is given 7 days prior to a scheduled clinic visit.

Volumes to be administered are shown in [Table 2](#). Please refer to the Study Drug Manual provided by the Sponsor or designee for more detailed instructions for Study Drug (ISIS 703802 or placebo) preparation and administration.

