#### **2.3.4 Clinical Experience**

Detailed information concerning the clinical studies conducted with ISIS 703802 can be found in the Investigator's Brochure. A summary is included below.

The Study Drug, ISIS 703802, is being evaluated in Phase 1 in the clinical setting with single doses up to 120 mg and multiple doses up to 60 mg (once per week for 6 weeks). The parent drug ISIS 563580, an unconjugated 2'-MOE modified ASO that has the same base sequence as ISIS 703802, was also evaluated in a blinded, placebo-controlled Phase 1 study.

An interim analysis of ISIS 703802 Phase 1 SAD/MAD Study (ISIS 703802-CS1) was performed in 44 subjects administered single ascending (20, 40 and 80 mg) or multiple ascending doses (10, 20, 40 and 60 mg/week for 6 weeks). Twelve participants were randomly assigned to single-dose groups (9 to active-agent dose groups and 3 to the placebo group) and 32 were randomly assigned to multiple-dose groups (24 to active-agent dose groups and 8 to the placebo group). The main endpoints of the study were safety, tolerability, pharmacokinetics, pharmacodynamics and changes in lipids and lipoproteins. After 6 weeks of treatment, persons in the multiple dose groups treated with ISIS 703802 had dose-dependent reductions in levels of ANGPTL3 protein (reductions of 46.6 to 84.5% from Baseline,  $P < 0.01$  for all doses vs. placebo 1.6%) and in levels of triglycerides (reductions of 33.2 to 63.1% vs placebo 11.4%), LDL cholesterol (1.3 to 32.9% vs placebo 13.6%), very-low-density lipoprotein cholesterol (27.9 to 60.0% vs placebo 4.0%), non-high-density lipoprotein cholesterol (10.0 to 36.6% vs placebo 9.1%), apolipoprotein B (3.4 to 25.7% vs placebo 11.0%), and apolipoprotein C-III (18.9 to 58.8% vs placebo 3.1%). There were no serious adverse events documented during the trial. No protocol-defined injection-site reactions were reported. Of those participants who received the multiple-dose regimen, three reported headache (one who received placebo and two who

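### The single 2-day rescheduling condition in Protocol Section 8.1 does not fit every-4-week dosing and, read literally, allows Cohort C 160 mg in two injections 2 days apart

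*Protocol*

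**What the plan says.** Protocol Section 8.1 lists the three regimens. Cohort A takes 20 mg weekly in 26 injections, and Cohort B takes 40 mg at 4-week intervals in 6 injections. The third entry reads: "Cohort C: a single SC dose of 80 mg once every 4 weeks for 21 weeks and 6 doses".

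The section adds that "subjects in Cohorts B and C should receive 1 dose every 4 weeks with weeks always defined relative to Study Day 1". It then covers departures from the schedule. The trigger is broad ("If a subject misses an injection, or if dosing on the usual day is not possible"), and the permission attached to it carries a single proviso: "the subject can reschedule the injection provided that 2 doses are administered at least 2 days apart". The sentence does not distinguish between cohorts, and the 2-day gap is its only condition. The next paragraph, also without distinction, says: "Every effort should be made to ensure the previous dose is given 7 days prior to a scheduled clinic visit".

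Three other places bear on spacing in Cohorts B and C:

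- The every-4-week Schedule of Procedures in Appendix A gives windows of ±2 or ±3 days for the post-Day 1 dosing visits. They are labelled as visit and testing windows, not dosing windows.
- Footnote o to that schedule places the last dose at Day 141 ±3 days.
- Section 8.6.4 asks for medical monitor approval of schedule changes. It does so under the severe hypoglycemia stopping rule, after a sentence on safety and tolerability.

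Section 2.3.4 describes Phase 1 of ISIS 703802 "with single doses up to 120 mg and multiple doses up to 60 mg (once per week for 6 weeks"). The interim results summarised there cover single doses of 20, 40 and 80 mg and weekly doses of 10 to 60 mg.

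**The concern.** A 2-day minimum gap and a 7-day interval before visits are natural for a weekly regimen. Stated for all cohorts, they sit badly with a 28-day regimen that carries up to four times the Cohort A dose per injection. A site or a self-administering subject who follows the rescheduling sentence exactly could give a very late dose and the next scheduled dose almost together. What is at stake is a short-interval amount in Cohort C that the protocol's own Phase 1 summary does not describe.

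Such an event need not be noticed. It complies with Section 8.1, so it need not be recorded as a dosing error under Section 9.5.3. Compliance in SAP Section 3.2.7 is calculated from volume, and the Per Protocol Set counts doses within 6 months, so neither looks at spacing.

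**Working it through.** **1. Reproduce the plan's dosing figures (Table 2 and Appendix A).** Total = dose × number of doses. Last dose day = 1 + interval × (doses − 1).

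| Cohort | Total | Last dose day |
|---|---|---|
| A | 20 × 26 = 520 mg | 1 + 7 × 25 = 176 |
| B | 40 × 6 = 240 mg | 1 + 28 × 5 = 141 |
| C | 80 × 6 = 480 mg | 1 + 28 × 5 = 141 |

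All agree with the protocol. Scheduled doses in Cohorts B and C fall on Days 1, 29, 57, 85, 113 and 141.

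**2. Apply the rescheduling condition literally.** The Day 29 dose is missed and given on Day 55, and the next dose is given on schedule on Day 57. The gap is 57 − 55 = 2 days, which complies. Day 139 followed by Day 141 also complies and respects the limit on the last dose.

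**3. Amount given in the two injections.**

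| Cohort | Two doses | Against 120 mg (largest Phase 1 single dose) |
|---|---|---|
| A | 2 × 20 = 40 mg | below |
| B | 2 × 40 = 80 mg | below |
| C | 2 × 80 = 160 mg | 160/120 = 1.33 times |

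For Cohort C, 160 mg is also 160/60 = 2.67 times the largest weekly dose and 160/80 = 2 times the largest single dose in the summarised interim data.

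**4. Compare cumulative dose.** The top Phase 1 multiple-dose regimen gave 60 × 6 = 360 mg over Days 1 to 36. With one make-up dose, a 36-day span in Cohort C holds at most three doses (for example Days 55, 57 and 85), or 3 × 80 = 240 mg. The excess therefore lies only in the amount given over a short interval.

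**5. Set the condition against the schedule.** Suppose the Appendix A visit windows did bind the doses. The smallest gap between consecutive doses would then be from Day 113 + 3 to Day 141 − 3, that is 138 − 116 = 22 days. The rescheduling sentence allows 2 days.

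**6. Test the 7-day sentence.** In Cohort A it fits: the Day 183 visit is 7 days after Day 176. In Cohorts B and C the main visits after Day 1 (Days 29, 57, 85, 113, 141 and 169) each fall 28 days after the previous scheduled dose. Applied to Day 169, the sentence would call for a dose on Day 162, against a last dose at Day 141 ±3. The exception is the PK-subgroup visit on Day 148, which is 141 + 7.

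**7. Interval from last dose to Week 25.** With the last dose at Day 141 ±3 and the visit at Day 169 ±3, the interval runs from 166 − 144 = 22 to 172 − 138 = 34 days. Rescheduling an earlier dose does not change these bounds.

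**The case against.** The strongest reply is that Section 8.1 should be read as a whole. It tells Cohorts B and C to dose every 4 weeks counted from Day 1. Pre-dose PK samples at each dosing visit tie injections to visits with narrow windows. Section 8.6.4 has an approval sentence. The Study Drug Manual, which is not available here, may add instructions. The worked example needs a dose 26 days late followed by one on time, and the Per Protocol Set accepts 5 of 6 doses, so it gives no reason to double up after one miss.

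Much of this stands on likelihood, and few subjects should be affected. It does not settle the text. The 4-week sentence says should, the windows are for visits and testing, the reach of the approval sentence beyond its section is arguable, and home administration is allowed. Missing platelet counts can themselves delay a dose (Sections 6.2 and 8.5.3).

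A reader might infer four stronger points that the documents do not support:

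- **That both every-4-week cohorts pass the Phase 1 maximum.** Only Cohort C does.
- **That 160 mg over 2 days equals an untested single dose.** It is two 80 mg injections. Section 2.3.4 reports a Tmax of 1 to 6 hours, a rapid disposition phase and no accumulation in Cmax or AUC after six weekly doses. The more than proportional rise it reports concerns single doses of 40 versus 80 mg, not repeated ones.
- **That the 7-day sentence can never apply to Cohorts B and C.** Day 148 is a counter-example, and the sentence asks only for best efforts.
- **That the Week 25 triglyceride result is compromised.** The limit on the last dose bounds the interval, and nothing in the documents quantifies an effect.

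**Conclusion.** The point holds in a limited form. One rescheduling condition, suited to weekly dosing, also governs the every-4-week cohorts, and no other text clearly overrides it. Followed literally, it permits 160 mg in 2 days in Cohort C. That is 40 mg above the largest Phase 1 single dose and is given faster than any regimen Section 2.3.4 describes. Each injection, and the cumulative dose over a comparable span, remain inside the Phase 1 range, and Cohorts A and B stay below 120 mg. The condition contradicts the intended 28-day spacing, and the 7-day sentence does not fit the main Cohort B and C visits.

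This rests on three assumptions: Section 8.1 is read as written, the visit windows do not bind the doses, and the Study Drug Manual adds no restriction. The cumulative comparison further assumes one make-up dose. The issue is one of safety wording with low expected frequency. It is not a demonstrated threat to the primary analysis.

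**What to change.** Reconcile the rescheduling condition and the 7-day sentence in Section 8.1 with the every-4-week schedule, the Appendix A visit windows, the Day 141 ±3 limit on the last dose and the Phase 1 range in Section 2.3.4. State both sentences separately for the weekly and the every-4-week regimens. Make clear whether the Appendix A windows apply to dosing and whether the approval sentence in Section 8.6.4 covers make-up doses, and check that the Study Drug Manual agrees. The intervals are for the sponsor's clinical team to set; no dose or interval is proposed here.

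The cost is protocol wording and a site memo, with no added subjects, visits or analyses.
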